- Low glycemic index meals should be eaten for approximately 48 hours after copanlisib infusion. For further guidance about mealtimes and glucose monitoring, please see **Sections 9.3 and 9.4** and the table of events in **Section 10** below.
- Please refer to **Table 11-13** and consider consultation with an endocrinologist for management of hyperglycemia.
- Blood pressure will be measured approximately every 5-10 minutes prior to each copanlisib dose until 2 consecutive results <150/90 mmHg are recorded. If blood pressure is 150/90 mmHg, the investigator can consider a medical intervention or can delay infusion of the study drug. The patient should rest before blood pressure is recorded.
- On infusion days, blood pressure will be measured at 0h (pre-dose), approximately 30 min (mid-infusion), approximately 60 min (end of infusion), and approximately 1 h after the end of infusion. **Note:** A window of ± 15 min is allowed for all blood pressure measurements, except for the 0 h (pre-dose) measurement.
- No dose should be given if blood pressure is 150/90 mmHg. Antihypertensive medication may be given to control increased blood pressure. Dosing can proceed on the scheduled day if at least 2 consecutive measurements <150/90 mmHg are recorded. In the absence of these measurements, dosing must be delayed.
- Patients will initiate a low-iodine diet preferably 7 days before initiation of the lesional dosimetry process, but minimally 5 days before initiation of the lesional dosimetry process (**Appendix C**).
- Patients will undergo a second biopsy while on therapy, unless the patient is exempt as defined in **Section 6.1**. When performing the second (on-treatment) biopsy, every attempt should be made to obtain tissue from the same tumor sampled at baseline (the pretreatment biopsy). Every effort will be made to perform the on-treatment biopsy on **Dtx15 or Dtx16** before the Thyrogen injection. However, the timing of the biopsy may be changed at the discretion of the Principle Investigator to account for patient preference and scheduling needs.

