- For patients who have sufficient uptake to warrant treatment with 1-131, the low-iodine diet must be continued for 2 days after administration of therapeutic 1-131 (1-131 activity administered for each patient will be guided by the calculated MTA). Vemurafenib will continue for 2 days after the administration of 1-131 therapy.
- For patients who did not meet the lesional dosimetry threshold required for treatment with 1-131, study drugs and low-iodine diet will be discontinued immediately, and a final tumor assessment will be performed. This includes not administering a second dose of copanlisib scheduled for **Day 15 (+/-1 day)** (these patients will have received only 1 dose of copanlisib).
- If there is evidence of disease progression before completing treatment with vemurafenib and copanlisib, study treatment with these drugs and 1-131 will be allowed to continue if the treating physician deems that such a decision is clinically justifiable.
- **Note:** *If no iodine uptake is detected* on the second 1-124 PET/CT scan done on **Dtx 12 (~2 days after 1-124)**, the subsequent 1-124 PET/CT scans (e.g., at ~3 and ~5 days after 1-124) and the planned blood sample collections for MTA determination does not have to be completed. If the degree of iodine uptake measured on the **Dtx 12 (~2 days after 1-124)** 1-124 PET/CT scan is determined to be insufficient for 1-131 therapy, the planned blood sample collections for MTA determination may not be completed; however, the subsequent 1-124 PET/CT scans (e.g., at ~72 and ~120 h after 1-124) may still be performed to evaluate iodine retention.
- If a patient is unable to receive the on-treatment Thyrogen-stimulated 1-124 PET/CT lesional dosimetry process for unanticipated reasons (e.g., weather delays, holidays, travel issues, personal conflicts, availability of tracer), performance of the 1-124 PET/CT protocol will be rescheduled to the following week. To avoid unnecessary drug exposure, vemurafenib and copanlisib can be stopped and restarted 3 days before the rescheduled administration of 1-124 tracer.
- **Note:** If feasible, tumor measurements (per RECIST v1.1) will be performed with CT scans (without iodinated contrast) and/or MRI scans at separate times from the 1-124 PET/CT scans according to the schedule in **Section 10.0**.

Figure 3. On-treatment and posttreatment schedule of events for patients with sufficient uptake to warrant treatment with 1-131.

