- Calcium channel blockers may be used to control preexisting hypertension. Nondihydropyridine calcium channel blockers (e.g., verapamil and diltiazem) should be avoided because of a potential interaction with CYP3A4.
- Short-term (up to 7 days) systemic corticosteroids >15 mg prednisone or equivalent will be allowed for the management of acute conditions (e.g., treatment of noninfectious pneumonitis [NIP]).

Prohibited concomitant therapy:

The following medications are prohibited during study treatment (see **Table 9-2** below).

This list is not comprehensive and is only meant to be used as a guide.

- Strong inhibitors or inducers of CYP3M/5
- Substrates of CYP3A4/5 with narrow therapeutic index
- Medications that carry a strong risk for QT prolongation
- Herbal medications/preparations (except for vitamins)
- Other investigational and antineoplastic therapies
- Anti-arrhythmic therapy other than beta blockers or digoxin
- Systemic corticosteroid therapy at a daily dose >15 mg prednisone or equivalent. Previous corticosteroid therapy must be stopped or reduced to the allowed dose at least 7 days before study registration. If a patient is on chronic corticosteroid therapy, corticosteroids should be de-escalated to the maximum allowed dose before the screening. Patients may be using topical or inhaled corticosteroids. Short-term (up to 7 days) systemic corticosteroids >15 mg prednisolone or equivalent will be allowed for the management of acute issues. The use of corticosteroids as antiemetics before copanlisib administration will not be allowed.
- Ongoing immunosuppressive therapy
- Concomitant radiotherapy
- Herbal medications, including but not limited to St. John's wort, Kava, ephedra (ma huang), ginkgo biloba, dehydroepiandrosterone (DHEA), yohimbe, saw palmetto, black cohosh, and ginseng. Patients should stop using all herbal medications at least 7 days before the first dose of study treatment.

Table 9-2: List of prohibited medications during the study

Category	Drug name
Strong CYP3A inhibitors	Voriconazole, boceprevir, clarithromycin, cobicistat, conivaptan, danoprevir/ritonavir, eltegravir/ritonavir, grapefruit juice, indinavir/ritonavir, itraconazole, ketoconazole, lopinavir/ritonavir, mibefradil, nefazodone, neflifavir, posaconazole, ritonavir, saquinavir, saquinavir/ritonavir, telaprevir, telithromycin, tipranavir/ritonavir, troleandomycin

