Moderate CYP3A inhibitors	Grapefruit, grapefruit hybrids, pum melos, star-fruit, Seville oranges (citrus paradisi fruit juice)
Strong CYP3A inducers	Avasimibe, carbamazepine, mitotane, phenobarbital, phenytoin, rifabutin, rifampin (rifampicin), St. John's wort (hypericum perforatum)
CYP3A substrates with narrow therapeutic index (NTI)	Alfentanil, apixaban (doses >2.5 mg only), aprepitant, astemizole, cisapride, cyclosporine, diergotamine, dihydroergotamine, ergotamine, fentanyl, lovastatin, nicardipine, nisoldipine, pimozide, quinidine, rivaroxaban, simvastatin, sirolimus, tacrolimus, terfenadine, thioridazine

Other investigational and antineoplastic therapies	Other investigational therapies must not be used while the patient is on the study. Anticancer therapy (chemotherapy, biologic or radiation therapy, and surgery) other than the study treatments must not be given to patients while the patient is on the study medication. If such agents are required for a patient, the patient must discontinue the study.
Herbal preparations/medications	Herbal preparations/medications are prohibited throughout the study. These herbal medications include but are not limited to St. John's wort, Kava, ephedra (ma huang), ginkgo biloba, dehydroepiandrosterone (DHEA), yohimbe, saw palmetto, and ginseng. Patients should stop using these herbal medications 7 days before the first dose of study medication.

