Note: Unless your doctor tells you differently, you must drink at least 8 to 10 8-ounce cups of fluid a day. This includes the drinks in the diet guidelines and as much water as you want.

Low-Iodine Diet Guidelines

Breads and Cereals

Total number of servings per day: 6-8

(1 serving equals 1 slice of bread or 1/2 cup of cooked pasta)

Include

Plain cooked barley, oats, millet, buckwheat, bulgur wheat, quinoa; unsalted, unprocessed, preservative-free boxed cereals, such as puffed rice and shredded wheat; rice, plain macaroni, spaghetti, noodles; cream of rice or cream of wheat hot cereals; unsalted rice cakes, unsalted plain matzah, English muffins, plain unsalted popcorn, homemade breads prepared without commercial dough.

Avoid

All commercial breads and rolls, processed boxed cereals, salted crackers, potato chips, pretzels, bagels, bialys, Melba toast, all other crackers, egg noodles, packaged rice, and pasta mixes.

Meat and Meat Substitutes

Total number of servings per day: 2-3

(1 serving equals 3 ounces of meat, fish, poultry, or 2 tablespoons of unsalted peanut or almond butter)

Include

Fresh beef, veal, pork, lamb, chicken and turkey; unsalted peanut or almond butter; fresh-water fish such as carp, river bass, lake trout, and river perch; fresh egg whites.

Avoid

Egg yolks and whole eggs, foods made with eggs; all fast foods; all canned fish such as salmon and tuna; seafood, shellfish (clams, crabs, oysters, lobsters), or any food made with fish stock; all processed meats; liver and all organ meats; all canned, dried, salted, or cured meats such as bacon, sausage, ham, frankfurters, chipped beef, luncheon meats (salami, bologna, pastrami); spicy meats such as chili, beef jerky, liverwurst; all canned or processed poultry such as turkey or chicken roll; tofu and soy products, such as soy burgers (e.g., Boca); salted peanut butter.

Milk and Milk Products

Total number of servings per day: 0

Include

None allowed.

Exception: Only 1 ounce of milk a day in your coffee or tea.

Avoid

All milk (except for 1 ounce daily) and milk products such as condensed or evaporated milk, cheese, yogurt, puddings, ice cream, custard; any cream such as heavy or light cream, whipped cream, sour cream; any foods made with cream or milk or cheese such as cream soup, pizza, and macaroni and cheese.

Fruits

Total number of servings per day: 5
(1 serving equals 1 small piece of fruit or 3/4 cup of juice)

Include

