All fresh fruit (exception: limit bananas to 1 serving per day); fresh apple sauce; all natural frozen fruits; fresh fruit juices (including bottles or cartons of fruit juice without artificial coloring or preservatives); white grape juice.

Avoid

Cranberries, all dried fruits, all canned fruits and canned fruit juices; jarred applesauce; cranberry and grape juice, canned or bottled cherries; rhubarb.

Vegetables

Total number of servings per day: 4
(1 serving equals 1/2 cup of cooked or 1 cup of raw vegetables)

Include

All fresh vegetables except spinach, fresh potatoes without skin, all plain frozen vegetables without added salt, fresh or dried legumes such as lentils and peas.

Avoid

All canned vegetables and all canned vegetable juices, fresh or dried beans such as red kidney beans, lima beans, navy beans, pinto beans and cowpeas; canned legumes (such as beans, peas, and lentils); canned soups; sauerkraut, celery; commercially prepared potatoes (e.g., instant mashed potatoes); frozen vegetables with added salt; spinach.

Fat

Total number of servings per day: 4-6
(1 serving equals 1 teaspoon of butter or oil)

Include

Unsalted margarine or sweet butter (not more than 1 teaspoon of each per day), oils, vegetable shortening, plain oil and white vinegar dressing.

Avoid

Salted nuts and seeds, mayonnaise, commercial salad dressings, and lard.

Beverages

Total number of servings per day: No restrictions
(1 serving equals 12 ounces of a carbonated beverage or 1 cup [8 ounces] of any of the other beverages listed)

Include

Water; bottled carbonated beverages without added coloring (such as Sprite, 7-Up, sodium-free seltzer); brewed coffee, tea steeped from tea leaves; white tea bags; fresh lemonade or fresh orangeade.

Avoid

Mineral water containing sodium; all bottled, canned, or powdered iced tea, lemonade, instant coffee, instant tea, instant iced tea, fruit punch, and other powdered or commercial drinks such as Hi-C and Kool-Aid; tea steeped from tea bags; soy milk and rice milk (which contain sea salt); ginger ale, Coke, Pepsi, or any other carbonated beverages with added coloring.

Desserts and sweets

Total number of servings per day: 2
(See below for serving equivalents)

Include

Each of the following equals 1 serving:

- 1 cup Knox clear gelatin
- 2 tablespoons sugar
- 2 tablespoons honey
- 2 tablespoons maple syrup
- 2 regular size marshmallows
- 1/2 cup natural sorbets with no coloring or added salt

Avoid

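### Appendix C permits fresh fruit of any kind and fresh juices during study treatment, and does not exclude the fruits and juices that Table 9-2 prohibits as CYP3A inhibitors

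*Combined protocol and SAP*

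**What the plan says.** **The diet sheet.** The Fruits entry of Appendix C sets 5 servings a day, where "1 serving equals 1 small piece of fruit or 3/4 cup of juice". Under Include it lists "All fresh fruit (exception: limit bananas to 1 serving per day); fresh apple sauce; all natural frozen fruits; fresh fruit juices". Under Avoid it lists "Cranberries, all dried fruits, all canned fruits and canned fruit juices; jarred applesauce; cranberry and grape juice, canned or bottled cherries; rhubarb".

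**The prohibition.** Section 9.5 introduces its list with "The following medications are prohibited during study treatment (see Table 9-2 below". In Table 9-2, the row for strong CYP3A inhibitors contains "eltegravir/ritonavir, grapefruit juice, indinavir/ritonavir". The row for moderate CYP3A inhibitors reads "Grapefruit, grapefruit hybrids, pum melos, star-fruit, Seville oranges (citrus paradisi fruit juice".

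**When the diet applies.** For the on-treatment dosimetry, Section 9.1 states: "Patients will initiate a low-iodine diet preferably 7 days before initiation of the lesional dosimetry process", with 5 days as the minimum, and refers to Appendix C. For patients treated with I-131, "the low-iodine diet must be continued for 2 days after administration of therapeutic 1-131". Patients below the dosimetry threshold stop the diet and the study drugs together. The diet footnote to Table 10-2 also sends the reader to Appendix C.

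**The concern.** Two parts of the protocol govern what the same patient may eat or drink on the same days, and they do not agree. Appendix C is the document about food. The fruit prohibition sits in a table titled as a list of medications, where someone advising on diet is less likely to look. Nothing in Appendix C, in the Section 9.1 diet instructions or in the Table 10-2 diet footnote links the two.

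What is at stake is mainly safety and protocol adherence. The protocol treats CYP3A inhibition as a concern: it prohibits strong inhibitors, and it advises against verapamil and diltiazem because of a potential CYP3A4 interaction. Tables 10-1 to 10-3 schedule no vemurafenib or copanlisib drug levels; the pharmacokinetic blood draws are for radioiodine. If a food did alter exposure, the planned assessments would not show it.

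**Working it through.** No sample size, power or event figure is involved. The check compares the two lists and then counts calendar days.

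**1. Are the Table 9-2 items excluded anywhere in Appendix C?**

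| Table 9-2 item | Row in Table 9-2 | Appendix C Include wording that admits it | On Appendix C Avoid list? |
|---|---|---|---|
| Grapefruit juice | Strong | Fresh fruit juices | No |
| Grapefruit, grapefruit hybrids | Moderate | Fresh fruit | No |
| Pummelos | Moderate | Fresh fruit | No |
| Star-fruit | Moderate | Fresh fruit | No |
| Seville oranges | Moderate | Fresh fruit | No |

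Bananas are limited to one serving, not barred. The Avoid entries (cranberries, rhubarb, dried and canned fruit, cranberry and grape juice, and others) include no fresh grapefruit-family item and no star-fruit. Appendix D, the glycemic-index food table, does not mention these fruits either.

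**2. Do the two lists apply on the same days?** Overlap in days = last common day − first common day + 1.

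Inputs on the nominal schedule:
- The on-treatment dosimetry process starts with Thyrogen on Dtx8 (Section 9.1). The diet therefore starts on Dtx8 − 7 = Dtx1, or on Dtx8 − 5 = Dtx3 with the minimum lead-in.
- I-131 is given on Dtx18, so the diet ends on Dtx18 + 2 = Dtx20. Vemurafenib runs Dtx1-20.
- Copanlisib is given on Dtx8 and Dtx15 (each ±1 day). Patients not given I-131 receive only the first dose, and their last vemurafenib dose is on day 12-15 (Table 10-2 footnote).
- The DLT window in Section 9.2 runs from the first copanlisib dose to 7 days after the last study drug. For I-131 recipients that is Dtx8 to Dtx20 + 7 = Dtx27, and 27 − 8 + 1 = 20 days.

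Results:
- *I-131 recipients, diet and vemurafenib:* 20 − 1 + 1 = 20 days (20 − 3 + 1 = 18 with the minimum lead-in). Both copanlisib infusions fall on diet days.
- *I-131 recipients, diet and DLT window:* Dtx8-20, so 20 − 8 + 1 = 13 of 20 days. With copanlisib ±1 day and I-131 on Dtx17 or Dtx18, the range is 11 days (Dtx9-19) to 14 days (Dtx7-20).
- *Patients not given I-131, diet and DLT window:* stopping on Dtx12 gives 12 − 8 + 1 = 5 days; stopping on Dtx15 gives 15 − 8 + 1 = 8 days. With copanlisib ±1 day the range is 4 to 9. These patients receive one infusion.

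The DLT monitoring footnote to Table 10-2 counts from the start of study treatment. Read that way, the window for I-131 recipients is Dtx1-27 and the overlap is 20 of 27 days. Section 9.2 is used here because it defines the DLT.

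**The case against.** The best reply is that nobody is told to eat a prohibited fruit. Include is a list of what is allowed, and a patient can satisfy both lists by choosing other fruit. The sample menu does so, naming orange juice, apple, orange and pear. Appendix C is a general institutional booklet, dated 1997 and last revised in 2008. It is about iodine, refers questions to a doctor or dietitian, and does not claim to cover drug interactions. A patient who ate grapefruit on treatment would be breaching Section 9.5, whatever the booklet allows.

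Much of this stands. The two passages are not opposite commands, and it would be wrong to say that patients are directed to eat these fruits or that bananas are the only restriction. But the wording goes beyond silence on interactions: it admits fresh fruit in general, and the patient avoids the conflict only if told about Table 9-2.

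Other passages do not close the gap. The exclusion criterion in Section 6.2 requires prohibited items to be held or replaced from at least 2 weeks before treatment until 1 week after the last dose, but it speaks of medication. Section 9.3 has the investigator manage the timing and content of caloric intake, but only on infusion days. Section 9.5 calls its list a non-comprehensive guide, which does not make the listed items permissible.

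A reader might go further and infer that the discrepancy threatens the MTD, because a 3+3 decision can turn on one DLT (0/3 becomes 1/3, 1/6 becomes 2/6). The documents do not support that step. They give no effect of these foods on vemurafenib or copanlisib exposure and no relation between exposure and DLT risk. The sensitivity of a 3+3 rule to one event is the same whatever causes the event.

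**Conclusion.** The inconsistency is real. Appendix C permits, during study treatment, fruits and juices that Table 9-2 prohibits over the same period, and no other passage resolves it. In I-131 recipients the two apply together for about 20 days on vemurafenib and 13 of the 20 DLT-window days. In patients not given I-131 the overlap with the DLT window is about 5 to 8 days. These counts assume the nominal schedule without dose interruption and the Section 9.2 window.

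The consequence is limited to this: a patient following the diet sheet alone could breach a protocol prohibition while on study drug. Any change in exposure, DLT count or MTD is unquantified and cannot be derived from the documents. No endpoint, sample size, decision rule or analysis changes. It merits correction because it bears on patient safety and costs almost nothing to resolve.

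**What to change.** Reconcile Appendix C with Table 9-2 so that the protocol gives one consistent fruit and juice instruction for the time on study drugs. Which content the reconciled instruction carries is for the sponsor and investigators to decide. Cross-reference it where Section 9.1 and the Table 10-2 diet footnote cite Appendix C, so that whoever hands out the diet sheet sees it.

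The cost is about two lines of text and a revised patient handout. Visits, samples, enrolment and analyses are unaffected.

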Appendix D: Glycemic Index Foods

Foods are categorized as having a low glycemic index if the glucose reference index is 55. High-glycemic-index foods have a glucose reference index >55. The summary table below contains glucose references for common foods.

High-carbohydrate foods		Breakfast cereals		Fruit and fruit products		Vegetables	
White wheat bread*	75 ± 2	Cornflakes	81 ± 6	Apple, raw†	36 ± 2	Potato, boiled	78 ± 4
Whole wheat/whole meal bread	74 ± 2	Wheat flake biscuits	69 ± 2	Orange, raw†	43 ± 3	Potato, instant mash	87 ± 3
Specialty grain bread	53 ± 2	Porridge, rolled oats	55 ± 2	Banana, raw†	51 ± 3	Potato, french fries	63 ± 5
Unleavened wheat bread	70 ± 5	Instant oat porridge	79 ± 3	Pineapple, raw	59 ± 8	Carrots, boiled	39 ± 4
Wheat roti	62 ± 3	Rice porridge/congee	78 ± 9	Mango, raw†	51 ± 5	Sweet potato, boiled	63 ± 6
Chapatti	52 ± 4	Millet porridge	67 ± 5	Watermelon, raw	76 ± 4	Pumpkin, boiled	64 ± 7
Corn tortilla	46 ± 4	Muesli	57 ± 2	Dates, raw	42 ± 4	Plantain/green banana	55 ± 6
White rice, boiled*	73 ± 4			Peaches, canned†	43 ± 5	Taro, boiled	53 ± 2
Brown rice, boiled	68 ± 4			Strawberry jam/jelly	49 ± 3	Vegetable soup	48 ± 5
Barley	28 ± 2			Apple juice	41 ± 2		
Sweet corn	52 ± 5			Orange juice	50 ± 2		
Spaghetti, white	49 ± 2						
Spaghetti, whole meal	48 ± 5						
Rice noodles†	53 ± 7						
Udon noodles	55 ± 7						
Couscous†	65 ± 4						

Dairy products and alternatives		Legumes		Snack products		Sugars	
Milk, full fat	39 ± 3	Chickpeas	28 ± 9	Chocolate	40 ± 3	Fructose	15 ± 4
Milk, skim	37 ± 4	Kidney beans	24 ± 4	Popcorn	65 ± 5	Sucrose	65 ± 4
Ice cream	51 ± 3	Lentils	32 ± 5	Potato crisps	56 ± 3	Glucose	103 ± 3
Yogurt, fruit	41 ± 2	Soya beans	16 ± 1	Soft drink/soda	59 ± 3	Honey	61 ± 3
Soy milk	34 ± 4			Rice crackers/crisps	87 ± 2		
Rice milk	86 ± 7						

Data are means ± SEM. *Low-GI varieties were also identified. †Average of all available data.

GI = glycemic index.

Appendix E: Permeability Glycoprotein (Pg-p) Substrates, Breast Cancer Resistance Protein (BCRP) Substrates, and Multidrug and Toxin Extrusion Protein 2 (MATE2K) Substrates

A list of drugs to be used with caution.

Copanlisib is an inhibitor of BCRP, P-gp and MATE2K in vitro . Therefore substrates, especially those with a narrow therapeutic range, should be used with caution . Pgp-Substrates	Aliskiren, ambrisentan, colchicine, dabigatran etexilate, digoxin ^a , everolimus, fexofenadine, imatinib, lapatinib, maraviroc, nilotinib, posaconazole, ranolazine, saxagliptin, sirolimus, sitagliptin, talinolol, tolvaptan, topotecan
BCRP substrates	Zidovudine, pantoprazole, cirnetidine, sulfasalazine, nitrofurantoin, ands everal s statins (lovas tatin, s irnvas tatin, cerivastatin, pitavastatin), mitoxantrone, methotrexate, topotecan, irnatinib, and irinotecan
MATE2K substrates	Metformin, cimetidine, procainamide and N methylnicotinamide

BCRP = Breast cancer resistance protein; MATE2K = Multidrug and toxin extrusion protein 2,

P-gp = Permeability glycoprotein

a:Narrow therapeutic window
